3.3. Screen failure

Screen failures are defined as participants who consent to participate in the clinical study but are not subsequently enrolled in the study. A minimal set of screen failure information is required to ensure transparent reporting of screen failure participants to meet the Consolidated Standards of Reporting Trials (CONSORT) publishing requirements and to respond to queries from regulatory authorities. Minimal information includes demography, screen failure details, and eligibility criteria.

Individuals who do not meet the criteria for participation in this study (screen failure) may not be rescreened.

3.4. Discontinuation of Study Intervention

Discontinuation of study product CX-4945/placebo does not mean discontinuation from the study, and the remaining study procedures will be completed as designated by this protocol. If a clinically significant finding is identified following the initiation of study treatment, the Investigator (or designee) will determine if any change in subject management is necessary. However, a subject should be discontinued from study product CX-4945/placebo in any of the following circumstances:

- A suspected Grade 3 or higher treatment-related AE (according to Common Terminology Criteria for Adverse Events (CTCAE) version 5.0)
- Any treatment-related SAE
- A subject receives baricitinib
- A subject receives warfarin
- The subject is pregnant

3.5. Discontinuation/Withdrawal from the Study

Subjects will be followed and monitored over the course of the study stated in **Section 5.1** Visit Schedule. If a subject does not attend any of the regularly scheduled visits, the subject will not be deemed as withdrawn, but the missed visit(s) will be considered as missing data in the study registry. Subjects may be discontinued from study product CX-4945 (**Section 3.4**) at the discretion of the Investigator if any severe, untoward effects occur to the subjects during the treatment phase. However, subjects may not be terminated from the study because of AEs.

If a subject, whether continuing study product CX-4945 or not, fails to return to any scheduled visits (i.e., lost to follow-up), or if the Investigator determines that it is in subject's best interest to be prematurely withdrawn from the study, the Investigator must determine the primary reason for subject's premature withdrawal and document this incidence in the eCRF, including the date of occurrence and the reason(s). All study-related information collected prior to subject's withdrawal will be retained and maintained in the study analysis unless otherwise explicitly requested by the subject; however, no further efforts will be made to obtain or record additional medical information about the subject. Subjects will be withdrawn from the study prematurely due to any of the following circumstances:

- Subject (or legal representative) decides to withdraw consent at any time.
- Subject, determined by the Investigator (or designee), is no longer physically or mentally feasible for further participation in the study.
- Subject is lost to follow-up.

- The sponsor terminates the study.

All collected/generated data and information about the subjects in the study prior to the time of study discontinuation will be recorded and analyzed, including the date and reason(s) to discontinue the study.

All subjects who have received at least one dose of study medication will be encouraged to complete all tests scheduled for the ET wherever possible at the time of the subject's withdrawal within 7 days.

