5.2.4. Efficacy Assessments

5.2.4.1. Hospitalization and Emergency Room Visit

If a participant is hospitalized or during emergency room (ER) visit, procedures and assessments will continue per the visit schedule. Hospitalization is defined as inpatient admission and more details are listed in **Section 5.2.5.6.** Hospitalization event will be followed up until Day 29.

This table describes discharge from hospital scenarios if an outpatient is subsequently hospitalized.

Table 5-2 Discharge from hospital (Outpatients Subsequently Hospitalized)

If hospital discharge...	Then....
Occurs prior to Day 29	Subjects will be asked to complete the remaining study assessments at the time points indicated in the visit schedule.
Occurs on the same day as a scheduled study visit	
If the scheduled study assessments are performed during hospitalization and the circumstances meet all the following criteria, assessments do not need to be repeated.
 
• The scheduled study assessments have been performed within 8 hours of discharge.• There has been no change in clinical status.• The information is available to the site.

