5.2.4.5. Mortality status

Mortality status will be followed up until Day 29 if applicable.

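### Protocol 3.5 ends active follow-up after any withdrawal or loss, apart from an encouraged early termination visit, and classifies non-attendance two ways, so primary events before Day 29 can be missed

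*Protocol*

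**What the plan says.** Protocol 2.1 defines the primary endpoint as the percentage of subjects with hospitalization, ER visit or death due to progression of pneumonia, from Day 1 to Day 29. Two assessment sections set the same horizon. Section 5.2.4.1 says "Hospitalization event will be followed up until Day 29", and 5.2.4.5 says "Mortality status will be followed up until Day 29 if applicable".

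Protocol 3.5 covers leaving the study early. Data already collected are kept, but "no further efforts will be made to obtain or record additional medical information about the subject". The paragraph applies to subjects who fail to return and to those whom the investigator withdraws. The listed reasons for withdrawal are withdrawn consent, being no longer physically or mentally able to take part, "Subject is lost to follow-up", and termination of the study by the sponsor. Only the first is a refusal by the subject.

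On non-attendance, the section opens with "If a subject does not attend any of the regularly scheduled visits, the subject will not be deemed as withdrawn"; the missed visit is to be missing data. The next paragraph describes a subject who "fails to return to any scheduled visits (i.e., lost to follow-up").

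Two provisions limit the stop. Dosed subjects who withdraw "will be encouraged to complete all tests scheduled for the ET wherever possible", within 7 days. Section 3.4 says "Discontinuation of study product CX-4945/placebo does not mean discontinuation from the study".

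Under SAP 3.2.3 and 3.3.2, a subject whose observation stops before Day 29 with no event seen is a Treatment Fail. SAP 3.2.11 tests the event rate including these subjects as a sensitivity analysis.

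**The concern.** A binary endpoint with a fixed 29-day window needs the status of every subject at Day 29. The usual safeguard is to separate leaving the visit schedule from refusing further follow-up, and to keep asking about death, admission and ER visits unless the subject refuses. Section 3.5 does not make this separation.

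The missingness may also depend on the outcome. A subject judged physically unable to continue, or one who stops attending because care has moved elsewhere, may be having the event that the trial counts. The two statements on non-attendance add to this: sites could handle identical subjects differently, with one kept under follow-up and the other closed out.

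The trial is small and SAP 3.4.1 reports too few events for logistic regression, so a few unresolved subjects could matter to the estimate.

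**Working it through.** **Passages side by side**

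1. *Scope of the stop.* It follows premature withdrawal for whatever reason. No contact attempt, record check or vital-status check after withdrawal appears in either document.
2. *What the ET visit recovers.* Protocol 5.1.5 makes Visit 5 the ET visit and has it record hospitalization, ER visits and mortality status. The intent-to-treat population also requires one dose, so the encouragement reaches everyone in the primary analysis. It recovers events up to that visit only. For a subject withdrawn on Day 7 with ET on Day 14, 29 − 14 = 15 days remain unobserved. If the same subject does not attend ET, 29 − 7 = 22 days do.
3. *Non-attendance.* Both sentences turn on the word any. If it means one visit, the same absence is first missing data and then loss. If it means all visits, the first sentence keeps in the study a subject whom the second calls lost. Under either single meaning the sentences conflict; they agree only if the word means different things in each.

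**The plan's attrition figure**

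- Inputs (Protocol 7.1): 120 evaluable, 10% attrition, about 136 enrolled.
- Simple inflation: 120 / 0.90 = 133.3, so 134. Rounding within four equal arms of 30 (an assumption): 30 / 0.90 = 33.3, so 34, and 4 × 34 = 136. The figure is reproduced.
- Evaluable means the modified per-protocol (mPP) set, which requires 80–120% of doses, visits through Visit 4 and no major violation. A subject removed for dosing can have full Day 29 data, and one lost after Visit 4 can remain in the set. The 10% is therefore not a rate of unknown Day 29 status.

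**Weight of each unresolved subject**

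- Inputs: 44 randomized (SAP 3.4.1), 1:1 allocation, so 22 per arm *assumed*.
- One subject: 1/22 = 4.5 points of an arm's event rate. With a 21/23 split: 1/21 = 4.8 and 1/23 = 4.3.
- If *k* per arm are unresolved, the risk difference can move by up to *k*/22 either way. This happens when all the unresolved in one arm had events and none in the other did.

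| Unresolved per arm (assumed) | Largest shift, points |
|---|---|
| 1 | 4.5 |
| 2 | 9.1 |
| 3 | 13.6 |

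**Illustration (event counts assumed, 22 per arm, Fisher's exact test, two-sided)**

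| Active vs placebo events | Situation | p |
|---|---|---|
| 0 vs 4 | as observed | 0.108 |
| 0 vs 6 | two unresolved placebo subjects had events | 0.021 |
| 2 vs 4 | two unresolved active subjects had events | 0.664 |

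**If loss is unrelated to outcome**

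Expected missed events = unresolved subjects × event rate × share of the window missed. With 4 unresolved and half the window missed, this is 4 × 0.02 × 0.5 = 0.04 at a 2% event rate and 4 × 0.20 × 0.5 = 0.40 at 20%. The size of the problem therefore depends on loss being informative.

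**The case against.** The strongest reply is that the plan protects follow-up more than the stop sentence suggests. The ET visit records every component of the endpoint. Subjects who only stop study drug stay in the study. Section 3.5 also says that subjects may not be terminated from the study because of adverse events, and 5.2.5.6 keeps admitted subjects in the study. Visits 3, 4 and 5 each ask about admissions and ER visits, so a later visit can pick up an event behind one missed visit. The two statements on non-attendance may be loose drafting, one meant for a skipped visit and the other for a subject who never comes back. The SAP foresees incomplete observation.

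Much of this stands, and it rules out several stronger readings:

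- A reader might infer that 3.5 stops all outcome collection. It does not; the ET visit is an exception.
- A reader might infer that the SAP counts these subjects as non-events in the main analysis. That is the apparent reading, but the text does not state it.
- A reader might apply 10% to 136 or to 44 to count the subjects affected. The attrition figure measures something else.
- A reader might conclude that events were in fact lost, or that the result is biased in a known direction. The documents give neither the number lost nor their arm.

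What survives is narrower. The ET visit is only encouraged, cannot capture later events, and is least likely to happen for a subject who is lost. It also sits awkwardly beside a statement that no further effort will be made. The visit-based safeguards help only subjects still regarded as in the study, and the non-attendance wording leaves that status unclear.

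**Conclusion.** The point holds as a design weakness of moderate weight. Section 3.5 states a rule that conflicts with the Day 29 horizon in 5.2.4.1 and 5.2.4.5 for subjects who leave early without withdrawing consent, and its wording on non-attendance is inconsistent. Primary events after the last contact or ET visit can go unrecorded, and the Treatment Fail analysis gives a sensitivity result, not the missing outcome.

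Assuming 22 per arm, the size is 4.5 points of an arm's event rate per unresolved subject. How many there are is unknown, and the shifts and p-values above are illustrations. If loss is unrelated to outcome, the expected number of missed events is below one under the assumptions shown. The sponsor stopped the study early (SAP 2.4), and sponsor termination is itself a withdrawal reason in 3.5; the documents do not say whether subjects then in follow-up were observed to Day 29.

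**What to change.** *Protocol wording, for any further version.* Reconcile 3.5 with 5.2.4.1 and 5.2.4.5:

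- Unless consent to follow-up is withdrawn, vital status, hospitalization and ER visits are sought to Day 29 by telephone or medical record, whatever the reason for leaving.
- A missed visit alone is missing data. Loss to follow-up is declared only after contact attempts up to Day 29 have failed.

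*This trial.* The last subject left on 22-APR-2025 and the SAP is dated 25-JUN-2025, so new wording cannot change follow-up. What remains practical is to query site records for deaths, admissions and ER visits to Day 29 where consent allows, blinded and before database lock if it is still open. The report should give, by arm, the number of subjects without complete Day 29 status and say how they were counted in the main analysis.

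*Cost.* Minor site effort, probably for a few subjects. A call or record may not always establish that an event was due to pneumonia progression, or that an ER visit lasted the 24 hours that 5.2.5.6 requires for recording. The consent terms are not visible in the documents and may limit the query.

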3.6. Method of Assigning Subjects to Treatment Groups

The study treatment will be randomly assigned to subjects. The randomized sequence of study treatments will be generated by a qualified biostatistician. The randomization schedule will be kept and maintained by the designated personnel before the study begins and until the database lock. The biostatistician prepares the schedule with a 1:1 randomization ratio (CX-4945: Placebo) by stratified randomization with study domains and study sites strata. Also, block permutation is used for generating randomization schedule. Eligible subjects will receive a random number at randomization. The subject will receive the corresponding treatment assigned by the EDC system. For any reason that a subject withdraws from the study prematurely after the randomization, his/her randomization number will not be reused. The next eligible subject will receive the lowest available randomization number.

3.7. Blinding

This is a double-blind study. Neither the subject nor the investigators, clinic administrators, or sponsor staff who involve in the treatment or clinical evaluation of the subjects will be aware of the treatment received either at the time of randomization or later, throughout the conduct of the trial. Assigned unblinded team may include study site stuff, CRO's personnel and/or Senhwa Biosciences, Inc's personnel. Other personnels involved in the study (the investigator and the clinical monitor) will be blinded until the database lock.

The treatment codes will not be prematurely broken unless an emergency situation, when the appropriate management of the subject necessitated acknowledgement of the treatment allocation, occurred. In the event of a medical emergency, if possible, the medical monitor should be contacted first to discuss the need for unblinding. For unblinding a subject, the treatment code blind can be obtained by the investigator, by accessing the EDC system.

The sponsor must be notified immediately if the treatment code blind is broken.

3.8. Concomitant Therapy

1. The following medication should be prohibited during the specified period:
 - (1) Warfarin is prohibited 14 days prior to screening and the treatment phase.
 - (2) Any other investigational treatment within 30 days before Screening and during study
2. The routine use of antibiotics is not recommended. Antibiotics may be used if bacterial infections are present or suspected. The type of antibiotic will be selected based on the subject's clinical disease status and symptoms with discretion of investigator.

4. TREATMENTS

4.1. Detail of Study Medication

4.1.1. Active drug

Study medication	CX-4945
Characteristics & Physical State	The isolated CX-4945 Sodium Salt is pale yellow to yellow solid which is formulated in an opaque blue, shell-gelatin capsule.
Dose(s)	200 mg/capsule
Dosage and Frequency	CX-4945 will be administered at 400 mg BID for 5 consecutive days starting on Day 1 in addition to SOC.
Administration route	Immediate release, oral administration
Mechanism of Action	CX-4945 is an inhibitor of Casein Kinase II (CK2) with anti-viral and anti-inflammatory effects. It interacts competitively with the ATP-binding site of CK2 subunit alpha, leading to the inhibition of several downstream signaling pathways.
Pharmacological category	Antiviral Drug
Storage	Store at temperature between 15-30°C.
Manufacturer	Senhwa Biosciences, Inc.

4.1.2. Placebo drug

Study medication:	CX-4945 Placebo
Characteristics & Physical State	The placebo drug is identical in appearance to the CX-4945 with the same excipient ingredients, but without the active compound.
Dose(s)	200 mg/capsule
Dosage and Frequency	The dosage and frequency are the same as active drug.
Administration route	Immediate release, oral administration
Storage	Store at temperature between 15-30°C.
Manufacturer	Senhwa Biosciences, Inc.

4.2. Dosage and Administration

Subjects will take two capsules of 200 mg CX-4945 or placebo, along with water twice daily on an empty stomach (preferably two hours after finishing a meal). It is recommended to take one capsule at a time with a 10-minute interval between each capsule to avoid a clumping effect. After taking the capsules, subjects are encouraged to avoid food intake, except for water, for at least 2 hours.

4.3. Packaging and Labeling

Packaging: CX-4945 are supplied as 200 mg strength auto-filled capsules (AFCs) in size 1, opaque blue capsules. Seventy (70) CX-4945 capsules (or placebo) are packaged in a 120 cc wide mouth round white HDPE bottle with a 38 mm cap with induction seal. The bottle contains a polyester coil and 1 g Sorb-IT® desiccant. Senhwa Biosciences will arrange the preparation, packaging and distribution of the study drugs.

Labeling: All study medication will be supplied in identical package, and the label will include the required regulatory agency caution statements, the protocol number, the Sponsor's identification, manufacturer's name, storage conditions, and expiry date.

4.4. Handling and Storage

The study medication will be handled by the investigator or the designated pharmacist for management and dispensation. All supplies for this study should be kept under adequate security and storage conditions. CX-4945 should be stored in the container provided, between 15 °C and 30 °C, as indicated on the label, and should be protected from moisture, freezing, and bright light

4.5. Supplies and Accountability

The investigator or the pharmacist will inventory and acknowledge receipt of all shipments of study medication. All study medication must be kept in a locked area with access restricted to designated study personnel. The study medication must be stored in accordance with the manufacturer's instructions. The investigator or pharmacist will also keep accurate records of the quantities of study medication dispensed and used by each subject. The site monitor will periodically check the supplies of study medication held by the investigator or the pharmacist to ensure accountability of all study medication used.

4.6. Treatment Compliance

Site staff will dispense study medications to all subjects ensuring proper administration of the investigational product (IP). Patients will be instructed on using ePRO to keep a dosing record for all dose administrations. Patients will be instructed to bring the dosing record and all unused study medication and empty study medication containers at Visit 3. The dosing record will be reviewed and the IP will be counted, documented, and recorded by site staff. The investigator or sub-investigator will check the compliance status of each patient based on the number of prescribed IP, number of returned IP, or number of lost IP, and describe compliance status in the medical record or other source documents, as well as checking data integrity in reference to the IP inventory at each visit.

5. STUDY CONDUCT

5.1. Visit Schedule

5.1.1. Visit 1 – Screening Visit (Day -2 ~ 1)

After a subject has signed the informed consent document, he or she will be enrolled after screening for selection criteria. The following assessments should be evaluated at this visit:

- (1) Obtain signed informed consent
- (2) Check subject's eligibility: inclusion and exclusion criteria
- (3) Collect demographic data
- (4) Collect general medical history
- (5) Conduct physical exam: It should be also recorded a complete physical exam, height, and weight
- (6) Measure vital signs
- (7) Collect NIAID 8-point ordinal scale
- (8) Assess pulse oxygen saturation: measure SpO₂ and record FiO₂
- (9) Perform 12-lead ECG
- (10) Perform chest X-ray
- (11) Collect urine and blood samples for the following laboratory tests
 - Hematology
 - Blood Chemistry
 - Coagulation
 - Urinalysis
- (12) Perform pregnancy test: Only for female with child bearing potential
- (13) Record Pneumonia Severity Index (PSI) risk class
- (14) Collect nasopharyngeal swab samples for rapid diagnostic test
- (15) Collect prior and concomitant medications

5.1.2. Visit 2 (Day 1) – Baseline, randomization, the first day of treatment

The following procedures should be evaluated at the visit:

- (1) Collect any change of medical history. Any pre-treatment medical events will be recorded as medical history
- (2) Conduct physical exam

- (3) Measure vital signs
- (4) Collect NIAID 8-point ordinal scale
- (5) Assess pulse oxygen saturation: measure SpO₂ and record FiO₂
- (6) Collect urine and blood samples for the following laboratory tests.
 - Hematology
 - Blood Chemistry
 - Coagulation
 - Urinalysis
 - Biomarker evaluations
- (7) Collect nasopharyngeal swab samples for RT-PCR
- (8) Randomization
- (9) Dispense study drug. The study drugs will be administered for 5 consecutive days starting on Day 1 and completing on Day 5, or on Day 6 if only one dose is administered on Day 1.
- (10) Provide SOC/supportive care (as needed)
- (11) Record any change of concomitant medication
- (12) Instruct the use of the Electronic Patient Reported Outcomes (ePRO) for dose administrations and body temperature record
- (13) Record hospitalization events and ER visit, if any
- (14) Check mortality status
- (15) Record adverse events after drug administration, if any

5.1.3. Visit 3 (Day 7 ± 1 Day) – The end of treatment (EOT)

The following assessments should be evaluated at this visit:

- (1) Conduct physical exam
- (2) Measure vital signs
- (3) Collect NIAID 8-point ordinal scale
- (4) Assess pulse oxygen saturation: measure SpO₂ and record FiO₂
- (5) Perform 12-lead ECG
- (6) Perform chest X-ray
- (7) Collect urine and blood samples for the following laboratory tests.
 - Hematology
 - Blood Chemistry
 - Coagulation

- Urinalysis
- Biomarker evaluations

(8) Perform pregnancy test: Only for female with child bearing potential

(9) Collect nasopharyngeal swab samples for RT-PCR

(10) Check ePRO completion status

(11) Provide SOC/supportive care (as needed)

(12) Check drug accountability and compliance. Return all unused study drugs and empty containers

(13) Record hospitalization events and ER visit, if any

(14) Record any change of concomitant medication

(15) Record adverse events and check mortality status, if needed

